### **10.1. Participant Information and Consent**

Biogen will only source data from registries that demonstrate protection of human participants and that have appropriate ethics approval and informed consent processes.

The data in the registry networks are collected based on participants' informed consent with the relevant registry network informed consent form or equivalent. The registry data will only be provided for use in this study in alignment with the existing registry consents and ethics approvals.

### **10.2. Participant Data Protection**

This is a non-interventional study using secondary data that poses minimal risks for participants, related only to data privacy. To address this risk, all data used in the study will be de-identified with processes in place to ensure there is no breach of confidentiality regarding personal identifiers or health information. Data protection and privacy regulations will be observed in collecting, forwarding, processing, and storing data from study participants by both the registry networks and Biogen.

### **10.3. Compensation for Injury**

Not applicable for secondary data study.

### **10.4. Conflict of Interest**

The contributing registries should address any potential conflicts of interest (e.g., financial interest in the Sponsor) as part of their approved study consent processes as appropriate.

CONFIDENTIAL

The information contained herein may not be used, disclosed, or published without the written consent of Biogen MA Inc.

## **11. MANAGEMENT AND REPORTING OF ADVERSE EVENTS/ADVERSE REACTIONS**

Not applicable. This study is secondary use of data and will follow relevant regulations. SAEs are collected per local and/or regional guidelines and requirements in the contributing registries.

CONFIDENTIAL

The information contained herein may not be used, disclosed, or published without the written consent of Biogen MA Inc.

## **12. PLANS FOR DISSEMINATING AND COMMUNICATING STUDY RESULTS**

The interim study reports will be available according to the schedule outlined in Section 6.

### **12.1. Notification of Study Completion or Termination**

Where required, the appropriate parties must be notified of completion or termination of this study and sent a copy of the final study synopsis in accordance with necessary timelines.

### **12.2. Registration of Study and Disclosure of Study Results**

Biogen will register the study and post study results, regardless of outcome, in the HMA-EMA catalogue of real-world data studies and on other publicly accessible websites in accordance with the applicable laws and regulations.

CONFIDENTIAL

The information contained herein may not be used, disclosed, or published without the written consent of Biogen MA Inc.

**14. ANNEX 1: LIST OF STAND-ALONE DOCUMENTS**

None.

CONFIDENTIAL

The information contained herein may not be used, disclosed, or published without the written consent of  
Biogen MA Inc.

## 15. ANNEX 2: ENCEPP CHECKLIST FOR STUDY PROTOCOLS (REVISION 4)

**Study title:** An observational registry-based study to evaluate the long-term safety of tofersen in people with *SOD1*-ALS

**HMA-EMA catalogue number:** Study not registered  
**Study reference number (if applicable):** Not Applicable

Section 1: Milestones	Yes	No	N/A	Section Number
1.1 Does the protocol specify timelines for				
1.1.1 Start of data collection 				6
1.1.2 End of data collection 				6
1.1.3 Progress report(s)				6
1.1.4 Interim report(s)				6
1.1.5 Registration in the HMA-EMA catalogue of real-world data studies				6
1.1.6 Final report of study results.				6

Comments:

1.1.3) As annual interim reports will be provided, other progress reports will not be delivered for this report.

Section 2: Research question	Yes	No	N/A	Section Number
2.1 Does the formulation of the research question and objectives clearly explain:				8.1
2.1.1 Why the study is conducted? (e.g., to address an important public health concern, a risk identified in the risk management plan, an emerging safety issue)				7.2
2.1.2 The objective(s) of the study?				8.2 8.3
2.1.3 The target population? (i.e., population or subgroup to whom the study results are intended to be generalised)				9.2.1
2.1.4 Which hypothesis(-es) is (are) to be tested?				
2.1.5 If applicable, that there is no a priori hypothesis?				9.7

 Date from which information on the first study is first recorded in the study dataset or, in the case of secondary use of data, the date from which data extraction starts.

 Date from which the analytical dataset is completely available.

CONFIDENTIAL

The information contained herein may not be used, disclosed, or published without the written consent of Biogen MA Inc.

Comments:

2.1.4) Statistical analyses will generally be descriptive in nature and there is no *a priori* hypothesis to be tested.

Section 3: Study design	Yes	No	N/A	Section Number
3.1 Is the study design described? (e.g., cohort, case-control, cross-sectional, other design)				9.1
3.2 Does the protocol specify whether the study is based on primary, secondary or combined data collection?				9.1
3.3 Does the protocol specify measures of occurrence? (e.g., rate, risk, prevalence)				9.1.1 9.1.2
3.4 Does the protocol specify measure(s) of association? (e.g., risk, odds ratio, excess risk, rate ratio, hazard ratio, risk/rate difference, number needed to harm [NNH])				
3.5 Does the protocol describe the approach for the collection and reporting of adverse events/adverse reactions? (e.g., adverse events that will not be collected in case of primary data collection)				11

Comments:

3.4) Statistical analyses will generally be descriptive in nature and no measures of association will be calculated.

Section 4: Source and study populations	Yes	No	N/A	Section Number
4.1 Is the source population described?				9.4
4.2 Is the planned study population defined in terms of:				
4.2.1 Study time period				9.2.3
4.2.2 Age and sex				9.2.1
4.2.3 Country of origin				9.2.2
4.2.4 Disease/indication				9.2.1
4.2.5 Duration of follow-up				9.2.3
4.3 Does the protocol define how the study population will be sampled from the source population? (e.g., event or inclusion/exclusion criteria)				9.2.1

Comments:

None.

CONFIDENTIAL

The information contained herein may not be used, disclosed, or published without the written consent of Biogen MA Inc.

Section 5: Exposure definition and measurement	Yes	No	N/A	Section Number
5.1 Does the protocol describe how the study exposure is defined and measured? (e.g., operational details for defining and categorising exposure, measurement of dose and duration of drug exposure)				9.3
5.2 Does the protocol address the validity of the exposure measurement? (e.g., precision, accuracy, use of validation sub-study)				
5.3 Is exposure categorised according to time windows?				
5.4 Is intensity of exposure addressed? (e.g., dose, duration)				9.3
5.5 Is exposure categorised based on biological mechanism of action and taking into account the pharmacokinetics and pharmacodynamics of the drug?				
5.6 Is (are) (an) appropriate comparator(s) identified?				

Comments:

5.2, 5.3, 5.5) Details on the specifics of exposure data capture in each registry network will be outlined in the SAP.

5.6) Tofersen is the recommended first-line treatment for people with progressive ALS caused by pathogenic mutations in *SOD1* [van Damme 2023] and an acceptable active comparator is lacking. There are currently no other approved therapies indicated for the treatment of *SOD1*-ALS.

Section 6: Outcome definition and measurement	Yes	No	N/A	Section Number
6.1 Does the protocol specify the primary and secondary (if applicable) outcome(s) to be investigated?				9.3
6.2 Does the protocol describe how the outcomes are defined and measured?				9.3
6.3 Does the protocol address the validity of outcome measurement? (e.g., precision, accuracy, sensitivity, specificity, positive predictive value, use of validation sub-study)				
6.4 Does the protocol describe specific outcomes relevant for Health Technology Assessment? (e.g., HRQoL, QALYs, DALYs, health care services utilisation, burden of disease or treatment, compliance, disease management)				9.3

Comments:

6.3) The protocol does not directly address the validity of outcome measurement. Nonetheless, the registry networks have harmonized common data elements to

CONFIDENTIAL

The information contained herein may not be used, disclosed, or published without the written consent of Biogen MA Inc.

increase validity, and each registry network has appropriate quality control to ensure the reliability of the data collected in them.

Section 7: Bias	Yes	No	N/A	Section Number
7.1 Does the protocol address ways to measure confounding? (e.g., confounding by indication)				9.1 9.7 9.9
7.2 Does the protocol address selection bias? (e.g., healthy user/adherer bias)				9.1 9.7 9.9
7.3 Does the protocol address information bias (e.g., misclassification of exposure and outcomes, time-related bias)				9.1 9.7 9.9

Comments:

None.

Section 8: Effect measure modification	Yes	No	N/A	Section Number
8.1) Does the protocol address effect modifiers? (e.g., collection of data on known effect modifiers, sub-group analyses, anticipated direction of effect)				9.9

Comments:

None.

Section 9: Data sources	Yes	No	N/A	Section Number
9.1 Does the protocol describe the data source(s) used in the study for the ascertainment of:				
9.1.1 Exposure? (e.g., pharmacy dispensing, general practice prescribing, claims data, self-report, face-to-face interview)				9.1
9.1.2 Outcomes? (e.g., clinical records, laboratory markers or values, claims data, self-report, patient interview including scales and questionnaires, vital statistics)				9.1
9.1.3 Covariates and other characteristics?				9.1
9.2 Does the protocol describe the information available from the data source(s) on:				
9.2.1 Exposure? (e.g., date of dispensing, drug quantity, dose, number of days of supply prescription, daily dosage, prescriber)				9.3
9.2.2 Outcomes? (e.g., date of occurrence, multiple event, severity measures related to event)				9.3

CONFIDENTIAL

The information contained herein may not be used, disclosed, or published without the written consent of Biogen MA Inc.

Section 9: Data sources	Yes	No	N/A	Section Number
9.2.3 Covariates and other characteristics? (e.g., age, sex, clinical and drug use history, co-morbidity, co-medications, lifestyle)				9.3
9.3 Is a coding system described for:				
9.3.1 Exposure? (e.g., WHO Drug Dictionary, Anatomical Therapeutic Chemical [ATC] Classification System)				9.3
9.3.2 Outcomes? (e.g., International Classification of Diseases (ICD), Medical Dictionary for Regulatory Activities (MedDRA))				9.7.1
9.3.3 Covariates and other characteristics?				9.7.2
9.4 Is a linkage method between data sources described? (e.g., based on a unique identifier or other)				

Comments:

9.4) No linkage between data sources.

Section 10: Analysis plan	Yes	No	N/A	Section Number
10.1 Are the statistical methods and the reason for their choice described?				9.7
10.2 Is study size and/or statistical precision estimated?				9.5
10.3 Are descriptive analyses included?				9.7
10.4 Are stratified analyses included?				9.7
10.5 Does the plan describe methods for analytic control of confounding?				9.9
10.6 Does the plan describe methods for analytic control of outcome misclassification?				9.9
10.7 Does the plan describe methods for handling missing data?				9.9
10.8 Are relevant sensitivity analyses described?				

Comments:

10.2) *SOD1*-ALS is a rare disease and as much data as possible will be collected but statistical analyses will be descriptive in nature.  
10.8) Further details will be provided in the SAP.

Section 11: Data management and quality control	Yes	No	N/A	Section Number
11.1 Does the protocol provide information on data storage? (e.g., software and IT environment, database maintenance and anti-fraud protection, archiving)				10.2

CONFIDENTIAL

The information contained herein may not be used, disclosed, or published without the written consent of Biogen MA Inc.

Section 11: Data management and quality control	Yes	No	N/A	Section Number
11.2 Are methods of quality assurance described?				9.8
11.3 Is there a system in place for independent review of study results?				9.8

Comments:

11.3) Of note, independent review of the study results is typically not required for studies of this nature.

Section 12: Limitations	Yes	No	N/A	Section Number
12.1 Does the protocol discuss the impact on the study results of:				
12.1.1 Selection bias?				9.9
12.1.2 Information bias?				9.9
12.1.3 Residual/unmeasured confounding? (e.g., anticipated direction and magnitude of such biases, validation sub-study, use of validation and external data, analytical methods)				9.9
12.2 Does the protocol discuss study feasibility? (e.g., study size, anticipated exposure uptake, duration of follow-up in a cohort study, patient recruitment, precision of the estimates)				9.8

Comments:

None.

Section 13: Ethical/data protection issues	Yes	No	N/A	Section Number
13.1 Have requirements of Ethics Committee/ Institutional Review Board been described?				10.1
13.2 Has any outcome of an ethical review procedure been addressed?				10.1
13.3 Have data protection requirements been described?				10.2

Comments:

None.

Section 14: Amendments and deviations	Yes	No	N/A	Section Number
14.1 Does the protocol include a section to document amendments and deviations?				5

Comments:

None.

CONFIDENTIAL

The information contained herein may not be used, disclosed, or published without the written consent of Biogen MA Inc.

Section 15: Plans for communication of study results	Yes	No	N/A	Section Number
15.1 Are plans described for communicating study results (e.g., to regulatory authorities)?				12
15.2 Are plans described for disseminating study results externally, including publication?				12.2

Comments:

None.

## **16. ANNEX 3: ADDITIONAL INFORMATION**

### **Definition of an SAE**

An SAE in this registry-based study protocol is any untoward medical occurrence, that, regardless of treatment status:

- results in death
- in the view of the healthcare provider, places the participant at immediate risk of death (a life-threatening event); however, this does not include an event that, had it occurred in a more severe form, might have caused death
- requires inpatient hospitalization or prolongation of existing hospitalization
- results in persistent or significant disability/incapacity
- results in a congenital anomaly/birth defect
- is a medically important event

A medically important event is an SAE that, in the opinion of the healthcare provider, may jeopardize the participant or may require intervention to prevent one of the other outcomes listed in the definition above. (Examples of such medical events include allergic bronchospasm requiring intensive treatment in an emergency room or convulsions occurring at home that do not require an inpatient hospitalization.)

CONFIDENTIAL

The information contained herein may not be used, disclosed, or published without the written consent of Biogen MA Inc.

## 17. ANNEX 4: DATA COLLECTED FOR SERIOUS ADVERSE EVENTS, PREGNANCY INFORMATION, AND TOFERSEN TREATMENT

### SAE Data

Variables	Data type / categories and responses
Report type	Initial
	Follow-up
SAE identifier 	
Report date	[date]
SAE date	[date]
Event name/term	Text field
SAE criteria	Death
	Life-Threatening event (this does not include an event that, had it occurred in a more severe form, might have caused death)
	Persistent or significant disability/incapacity
	Congenital anomaly/birth defect 
	Important Medical Events
	Hospitalization or prolongation of existing hospitalization
	Admission date: [date]
	Discharge date: [date]
Relationship to Tofersen	Not related
	Related
	Unknown
	Not applicable
Action taken with Tofersen treatment	No action
	Permanently withdrawn
	Temporarily suspended
	Unknown
	Other, Specify:
Outcome of SAE	Recovered/Resolved
	Recovered/Resolved with sequelae (prompts Text Field for Sequelae)
	Not recovered/not resolved
	Fatal
	Unknown

CONFIDENTIAL

The information contained herein may not be used, disclosed, or published without the written consent of Biogen MA Inc.

Variables	Data type / categories and responses
Date of outcome	[date]
Sequelae	Text field

Event identifier/ID for ease tracking event longitudinally and cross-form reference

Prompt pregnancy form

**Pregnancy data**

Variables	Data type / categories and responses
Date pregnancy confirmed	[date]
Data of last menstrual period	[date]
Ectopic pregnancy	Y/N
Date of outcome	[date]
Outcome	Live birth without congenital anomaly
	Live birth with congenital anomaly
	Premature birth
	Spontaneous abortion/miscarriage
	Elective termination
	Stillbirth
	Unknown

CONFIDENTIAL

The information contained herein may not be used, disclosed, or published without the written consent of Biogen MA Inc.

**Tofersen treatment log**

Variables	Data type / categories and responses
Treatment start date	[date]
Infusion dates	[date]
Dose	[numeric]
Dose unit	[Text field, values predefined]
Dose change	Y/N
Reason for dose change	[Text field]
Treatment discontinuation	Y/N
Treatment discontinuation date	[date]
Reason for discontinuation	Death 
	SAE 
	Healthcare provider decision
	Patient preference
	Other Specify [text field]
	Unknown

Details captured on mortality form

Prompt to SAE form

CONFIDENTIAL

The information contained herein may not be used, disclosed, or published without the written consent of Biogen MA Inc.

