### 7.2. Study Rationale and Regulatory Background

This study is part of the planned pharmacovigilance activities for tofersen (tradename: Qalsody™). Qalsody has been approved in multiple regions, including by both the United States Food and Drug Administration (US FDA) (April 2023) and the EMA (May 2024). In Europe, Qalsody was granted marketing authorisation (MA) under exceptional circumstances with the indication of treatment of adults with ALS associated with a mutation in the *SOD1* gene. As part of the conditions of the MA under exceptional circumstances, the marketing authorisation holder (MAH) agreed to conduct and submit the results of this observational registry-based study (Study 233AS401), to further evaluate the long-term safety of tofersen in people living with *SOD1*-ALS. This specific obligation is included as a Category 2 study in the EU risk management plan (RMP).

The safety and efficacy of tofersen was assessed in clinical trials and has a positive benefit/risk profile in the treatment of adults with *SOD1*-ALS. However, information on long-term use is limited. Given this and the rarity of the indication, this non-interventional registry-based study is being conducted as part of the post approval pharmacovigilance activities to further evaluate the long-term safety of tofersen among people with *SOD1*-ALS under routine medical care.

The safety profile is based on 166 participants with ALS (162 with *SOD1*-ALS) that were exposed to any dose of tofersen in the clinical development programs. Of these, a total of

CONFIDENTIAL

The information contained herein may not be used, disclosed, or published without the written consent of Biogen MA Inc.

147 people with *SOD1*-ALS received tofersen 100 mg, for 368.83 participant-years. The median exposure for this group was 148.4 weeks. Most adverse events (AE) reported during treatment with tofersen were consistent with the types and severities of AEs seen in people with *SOD1*-ALS or events observed in the context of the lumbar puncture (LP) procedure.

In the clinical studies, serious neurological events of myelitis, radiculitis, increased intracranial pressure, papilloedema, and aseptic meningitis have been reported in participants receiving tofersen and not in placebo treated participants. Details on these serious reactions are included in the EU product information.

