## 8. RESEARCH QUESTION AND OBJECTIVES

### 8.1. Research Question

The study's research questions are related to characterizing the long-term safety and tolerability of tofersen in routine clinical practice among adults with ALS who have a mutation in the *SOD1* gene.

All objectives will be stratified by tofersen treatment status except secondary objective 2 (assessed among tofersen users only). All data will be summarized by descriptive statistics.

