#### **9.7.2.2. Treatment Discontinuation**

Summary statistics of the duration of treatment use and prescribed dosing frequency will be provided among people with *SOD1*-ALS receiving tofersen. Frequency and proportion of participants with treatment discontinuation will be reported. Reported reason for treatment discontinuation will be tabulated.

CONFIDENTIAL

The information contained herein may not be used, disclosed, or published without the written consent of Biogen MA Inc.

[REDACTED]

[REDACTED]

[REDACTED]

[REDACTED]

[REDACTED]

[REDACTED]

[REDACTED]

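### The tofersen treatment log has no coded discontinuation reason for a non-serious adverse event, so the tabulated reasons may understate stopping for intolerance

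*Protocol*

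**What the plan says.** Section 8.1 of the protocol frames the research question as "characterizing the long-term safety and tolerability of tofersen in routine clinical practice". Secondary objective 2 (Section 8.3) is the frequency of treatment discontinuation among treated participants. The matching endpoint in Section 9.1.2 adds a listing of the reported reasons, and Section 9.7.2.2 states: "Reported reason for treatment discontinuation will be tabulated".

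The reasons come from the tofersen treatment log in Annex 4 (Section 17). It lists death, SAE, "Healthcare provider decision", "Patient preference", a residual option with a text field, and unknown. The SAE option carries the footnote "Prompt to SAE form". The provider and patient options show no text field. Annex 4 otherwise contains an SAE form and a pregnancy form, and no form for non-serious events. The item on action taken with tofersen sits on the SAE form.

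Section 7.2 says most adverse events in the clinical programme were of the types and severities seen in the disease or were "events observed in the context of the lumbar puncture (LP) procedure".

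**The concern.** The list of reasons mixes two dimensions. Death and SAE say why treatment ended; the provider and patient options say who ended it. A stop for a non-serious reaction is always also somebody's decision, so both of those options fit it literally, and the log as shown has no rule that cause comes first.

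This matters because tolerability is part of the research question while event collection in Annex 4 is confined to serious events. Below the SAE threshold, discontinuation and its reason is the main structured route to tolerability. If some intolerance-led stops are filed under provider or patient, the table shows too few adverse-event-led stops and too many that look like choice. The error runs in one direction, towards tofersen appearing better tolerated. For those entries an analysis plan cannot restore a cause that the form did not ask for.

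**Working it through.** The plan gives no figure to reproduce here. The first part of the check is a comparison of the form with the endpoint it feeds; the second is an illustration of size.

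**1. Classify the six options (Annex 4, tofersen treatment log).**

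| Option | What it records | Text field or prompt shown |
|---|---|---|
| Death | cause | mortality form |
| SAE | cause, serious events only | SAE form |
| Provider decision | who decided | none |
| Patient preference | who decided | none |
| Other | free | text field |
| Unknown | nothing | none |

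Of six options, one is an adverse-event reason, none is for a non-serious event, two name the decision-maker, and one is free text that can hold the cause.

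**2. Where can a stop for a non-serious event go?** Three options fit: provider, patient and other. Only the last keeps the cause.

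**3. What reaches the table?** Section 9.7.2.2 tabulates the reported reasons. The number and proportion discontinuing do not depend on which reason is ticked, so they are unaffected. Only the split between reasons is.

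**4. Size.**
- Treated participants, from Section 9.5: 25 cases per year × 5 years = 125; 125 × 0.40 = 50.
- Number stopping while alive: not given in the protocol. Assume 10 to 20.
- Share of those stopping for a non-serious reaction: not given. Assume 20% to 50%.
- Share of those filed under provider or patient instead of other: not given. Assume 50% to 100%.

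Affected = number stopping × share non-serious × share misfiled.
- Low: 10 × 0.20 × 0.50 = 1, and 1/50 = 2% of the treated group.
- High: 20 × 0.50 × 1.00 = 10, and 10/50 = 20% of the treated group.

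The third factor matters. With every such stop misfiled the range is 2 to 10 participants (10 × 0.20 = 2; 20 × 0.50 = 10). With half of them written in under other it is 1 to 5 (2 × 0.50 = 1; 10 × 0.50 = 5).

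**The case against.** The strongest reply is that the form already has a place for the cause: "Other Specify [text field" can hold a non-serious adverse event, so misfiling is possible but not forced. That is correct, and how sites would choose among the fitting options is not something the protocol tells us.

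Second, the stated objective and endpoint promise only the frequency of discontinuation and the reported reasons, and the form supplies both. Duration of use and prescribed dosing frequency are also planned (Section 9.7.2.2), and the log records infusion dates, dose changes and a free-text reason for a dose change. A reader might infer that the tolerability question cannot be answered at all, or that the table must show no discontinuations for non-serious events. The document supports neither reading. What is weakened is the attribution of stops to non-serious intolerance.

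Third, the SAE definition in Annex 3 includes medically important events, so some significant reactions without hospitalization would be captured under SAE. This narrows the gap but does not close it.

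Fourth, Section 7.2 does not say that the procedure-related events were non-serious or that anyone stopped because of them. It makes such stops plausible, no more.

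Fifth, Section 9.6 calls Annex 4 a summary, so the full registry forms may carry sub-fields that are not shown. If they do, the point reduces to saying so in Annex 4 and using those fields in the table.

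Last, these are registry data in secondary use, and forms change only within registry governance (Section 9.8). That bears on effort rather than feasibility: Section 9.4 says both networks were engaged to implement treatment and SAE data collection before the study starts, and Section 9.8 allows the sponsor to work with them on supplementing their processes.

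**Conclusion.** The point holds as a gap in the coded reasons. Annex 4 shows no structured discontinuation reason for a non-serious adverse event, and two of its options describe the decision-maker and not the cause. Stops for non-serious intolerance may be scattered across provider decision, patient preference and free text, so the planned tabulation may understate adverse-event-led discontinuation. The all-cause count stands.

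The size cannot be derived from the protocol. The 1 to 10 participants (2% to 20% of about 50) rest on assumed stopping rates, an assumed share for non-serious reactions and an assumed misfiling share of half to all; only the 50 follows from the protocol's own planning figures. The endpoint is secondary and descriptive with no planned comparison, so this is a correction worth making to one table and not a threat to the study. It is best made early, because later analysis cannot substitute for it.

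**What to change.** In the Annex 4 tofersen treatment log, add one coded reason: adverse event (non-serious), specify. Add an instruction that, where a cause is known, it takes precedence over who made the decision. A short underlying-reason field under the provider and patient options would serve in place of that instruction. If the full registry forms already hold such a field, state this in Annex 4.

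In Section 9.7.2.2, tabulate discontinuation due to any adverse event, serious or non-serious, as its own line, with the free-text entries under other reviewed and assigned to it where they name an event.

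The cost is a small form change in two registry networks, subject to their governance, preferably in place before extraction starts (planned for 30 January 2026, Section 6). Entries already made under the present list cannot be split, so the table should show them separately or carry a note.
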